#### 5.7.2.5 Demographics and baseline assessments

Demographics and baseline assessments include:

- Informed consent date
- Date of birth
- Gender
- Initials
- Ethnic origin
- Inclusion and exclusion criteria
- Relevant medical history/concurrent diseases
- Previous surgery, tissue augmenting therapy or revitalization treatments performed in the hands and products used if applicable.
- Concomitant medications and treatments
- Pregnancy test (for women of childbearing potential)

#### 5.7.3 Instruction of Device Use

Restylane Vital and Restylane Skinboosters Vital Lidocaine are injectable, sterile, transparent, biodegradable gels of non-animal crosslinked sodium hyaluronate. Restylane Skinboosters Vital Lidocaine has the addition of lidocaine hydrochloride. They are supplied in a glass syringe. Restylane Skinboosters Vital Lidocaine has a built in dose-guide, Smart Click System, which when activated creates a clicking sound and haptic feedback to indicate each injected dose. The 1 mL syringe gives approximately 100 such doses of 10 µL each. The contents of the syringe are sterilized using moist heat. The products are for single patient and single session use only. Disposable 29G needles sterilized using ethylene oxide are provided.

In terms of the Instruction of use for Restylane Vital, please see co-packed Restylane Vital IFU.

##### 5.7.3.1 Assembly of needle to syringe for Restylane Skinboosters Vital Lidocaine

Improper assembly may result in separation of the needle and syringe during injection. A strict

 EST. 1981	Title 43CH2305 CSP Vital-Lido-Hand-2w	Doc id MA-57336
---	---	---------------------------

[figure not shown]
aseptic technique must be followed during the assembly procedure described below.

- 1) Put on medical gloves.
- 2) Use your thumb and forefinger to hold firmly around both the syringe-barrel and the luer-lock adapter part (C) of the closure system, see Picture below.
- 3) With your other hand, take hold of the tip cap (A) at the end of the closure system and bend (do not rotate) until the cap disconnects and can be pulled off (tamper proof seal will be broken), see Picture below.
- 4) Do not touch the syringe tip (B) to keep it sterile, see Picture below.
- 5) Open the needle and grasp the needle shield.
- 6) Assure to hold both the syringe barrel and the luer-lock adapter (C), see Picture below.
- 7) To facilitate proper assembly, both push and rotate the needle firmly clockwise.
- 8) Make sure the needle is screwed on all the way so that the needle shield touches the luer lock adapter (C), see Picture below.
- 9) To remove the needle shield, hold the syringe and the luer lock adapter. With your other hand hold the needle shield and pull straight out. Do not rotate.

#### 5.7.3.2 Treatment Procedure for Restylane Skinboosters Vital Lidocaine

- 1) Prior to treatment, a medical history should be obtained for proper patient selection. The patient shall be informed about the indications, precautions, treatment responses, potential adverse events, and advised to contact a healthcare professional if they experience anything unusual at the treatment area.
- 2) Clean the treatment site thoroughly with a suitable antiseptic solution.
- 3) To avoid breakage of the needle, do not attempt to bend it before or during treatment. If the needle gets bent, discard it and complete the procedure with a replacement needle.
- 4) This product should be injected in the dermal layer of the skin, preferably in the deeper part of dermis. The injection technique and the administered quantity may vary. The multi puncture technique or short linear technique can be used.
- 5) Before injecting, remove the air by pressing the rod carefully until a small droplet is visible at the tip of the needle.
- 6) If desired, the Smart Click System is activated by pressing down the button located on the finger grip (D) until it locks into place, see Picture.
- 7) When the Smart Click System is switched on, again press the plunger rod carefully until the first click is heard to prime the system before use and to avoid a slightly larger volume of the first dose injected when the system is initially activated. The Smart Click System can be deactivated at any time by pushing the button in the finger grip upwards. It should be noted that it is not possible to perform an aspiration manoeuvre when the Smart Click system is activated.
- 8) When using the multi puncture technique it is recommended to inject approximately 20 µL (i.e. 2 clicks if the Smart Click System activated) per injection, 0.5 - 1 cm apart.

- 9) The gel should be evenly distributed in the areas where treatment is needed.
- 10) Do not apply excessive pressure to the syringe at any time. Presence of scar tissue may impede advancement of the needle. If resistance is encountered the needle should be partially withdrawn and repositioned or fully withdrawn and checked for function.
- 11) If immediate blanching occurs, the injection should be stopped and the area massaged until it returns to a normal colour. Blanching may represent a vessel occlusion. If normal skin colouring does not return, do not continue with the injection.
- 12) It is recommended to change needle for each new treatment site or following multiple punctures to avoid use of blunt needles and minimize the risk of infections.
- 13) A too large volume or a too superficial injection may give bumps on the treatment site.
- 14) Treated areas can be gently massaged after the injection if any irregularities are noted.

#### 5.7.3.3 Treatment Area and Treatment Regimen for Restylane Skinboosters Vital Lidocaine

The study product is intended for injection in the dorsal hand. Disposable 29G x  $\frac{1}{2}$ " TW needles should be used for both study products. Study product should be injected in the dermal layer of the skin, preferably in the deeper part of dermis. Allowed injection techniques are; multipuncture or short linear. Inject slowly while pulling the needle backwards.

No more than 20  $\mu$ L should be injected per injection point when using the multipuncture

 EST. 1981	Title 43CH2305 CSP Vital-Lido-Hand-2w	Doc id MA-57336
---	---	---------------------------

technique. Slowly inject 20  $\mu$ L droplets in the dermal layer of the skin, spacing droplets 0.5-1.0 cm apart to cover the entire treatment area. 20  $\mu$ L equals to 2 clicks when injecting with the smart click function activated on the Restylane Skinboosters Vital Lidocaine syringe.

The volume for each treatment should be adjusted depending on the subject's need and a volume of 0.5-1 mL for one hand per treatment session will be allowed. The same volume should be used for both hands.

#### 5.7.3.4 Post-treatment care

No topical or local anesthetic or other pain-relieving medication should be used before all VAS assessments are completed.

Ice for pain relief is allowed after all VAS evaluation is completed.

If any irregularities are noted after the use of ice pack, the treated area can be massaged again. A cream can be used during massage at the discretion of the investigator.

The subjects will be asked to avoid intensive physical stress (training) or intensive manual activities involving the hand, extensive heat (sauna)/sun or extreme cold in the first 2 days after the treatment .

The subjects will also be asked to avoid extensive exposure to potential skin irritants (e.g. cosmetics or laundry detergent) that could affect the skin in the treated area before the skin has healed completely in order to prevent infections.

#### 5.7.4 Instruction of Concomitant Treatment

Except as noted below, concomitant medications or other treatments or procedures may be utilized when the PI or his/her authorized designee considers it medically necessary.

Information regarding any use of concomitant medications, including over-the-counter medications administered during the study is to be recorded in the eCRF. The generic name or the trade name of all concomitant medication or a description of the procedure and the reason for its use shall be documented in the eCRF.

The following medications, treatments, and procedures are restricted or prohibited during the study:

- Concomitant treatment with chemotherapy, immunosuppressive agents, immunomodulatory therapy (e.g., monoclonal antibodies) is prohibited.
- Long term concomitant treatment with systemic or topical (on dorsal hands) corticosteroids are prohibited (inhaled corticoids are allowed). Corticosteroids should be used with caution and should be adjudged as necessary by the Investigator.
- Use of systemic or topical (on the dorsal hands) retinoic acid is prohibited.
- Planned hand surgery including sclerotherapy is prohibited.

 EST. 1981	Title 43CH2305 CSP Vital-Lido-Hand-2w	Doc id MA-57336
---	---	---------------------------

- Participation in any other clinical study within 30 days of baseline and during the study conduct is prohibited.

If a subject has used any of the above prohibited medications or performed any of the above prohibited procedures, a protocol deviation will be documented. The subject should continue in the study for the scheduled follow-up visits.

## 5.8 Bias Control Measures

### 5.8.1 Randomization and Blinding

#### 5.8.1.1 Randomization

Approximately 90 subjects will be randomized to determine which hand to receive treatment with Restylane Skinboosters Vital Lidocaine, and Restylane Vital to the other hand. Before starting the study, a computer-generated randomization list will be prepared under the supervision of a designated statistician.

Each subject will be assigned a subject number as they arrive for the treatment visit. Randomization will be assigned via the eCRF system. The treatment information will be kept by the Treating Investigator during the study not to be disclosed to the subjects.

#### 5.8.1.2 Treatment Blinding

Only the subject will be blinded. Treating Investigator will not be blinded to the treatment assignment.

The Treating Investigator is not allowed to discuss treatment assignment per hand with the subjects. All documents with information on study products shall be kept in a separate binder not available to the subjects.

To ensure the subject is kept treatment-blind the following measures are to be employed at the study site when injecting:

The same injection techniques, volume per injection point and similar total volume should be used for both hands as described above.

At the discretion of the investigator, the subject can listen to white noise/music in headphones during the treatment to cancel out the click sounds from the syringe when injecting Restylane Vital Skinboosters Lidocaine.

The injection will be performed behind a screen to prevent the subject from seeing the type of syringe used in order to achieve subject blinding.

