Comparator Product:	
Restylane Vital
 
Composition:
 
 
• Crosslinked sodium hyaluronate 20 mg/mL
 
• Phosphate buffered saline pH 7 ad q.s. 1 mL
 
 
Produced from pharmaceutical grade sodium hyaluronate and crosslinking agent BDDE.
 
Restylane Vital will be provided in a glass syringe containing 1 ml of gel. The study sites will be provided with disposable sterile 29G x ½" TW needles for use in the study.

Treatment area/ Treatment regimen/ Mode of administration:	
The study product is intended for injection in the dorsal hand. Disposable 29G x ½" TW needles should be used for both study products. Study product should be injected in the dermal layer of the skin, preferably in the deeper part of dermis. Allowed injection techniques are; multipuncture or short linear. Inject slowly while pulling the needle backwards.
 
No more than 20 µL should be injected per injection point when using the multipuncture technique. Slowly inject 20 µL droplets in the dermal layer of the skin, spacing droplets 0.5-1.0 cm apart to cover the entire treatment area. 20 µL equals to 2 clicks when injecting with the smart click function activated on the Restylane Skinboosters Vital Lidocaine syringe.
 
The volume for each treatment should be adjusted depending on the subject's need and a volume of 0.5-1 mL for one hand per treatment session will be allowed. The same volume should be used for both hands.
 
Treatment Blinding
 
To ensure the subject is kept treatment-blind the following measures are to be employed at the study site when injecting:
 
 
- The same injection techniques, volume per injection point and similar total volume should be used for both hands as described above.
 
- At the discretion of the investigator, the subject can listen to white noise/music in headphones during the treatment to cancel out the click sounds from the syringe when injecting Restylane Vital Skinboosters Lidocaine.
 
- The injection will be performed behind a screen to prevent the subject from seeing the type of syringe used in order to achieve subject blinding.
 
 
Post-treatment care
 
No topical or local anesthetic or other pain-relieving medication should be used

 GALDERMA EST. 1981	Title 43CH2305 CSP Vital-Lido-Hand-2w	Doc id MA-57336

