### 3.5.5 Warnings and Precautions

#### 3.5.5.1 Warnings

- Use at specific sites where there is active disease, such as inflammation (skin eruption such as cysts, pimples, rashes or hives), infection or tumours, in or near the intended treatment site should be avoided until the underlying process has been controlled.
- Restylane Skinboosters Vital Lidocaine is only intended for use as an intradermal implant. The product should not be used for breast site injections.
- This product must not be injected intramuscularly or intravascularly. Localized superficial ischemia and necrosis with potential scarring may occur after injection in or near vessels. It is thought to result from the injury, obstruction, or compromise of blood vessels. Special caution should be taken if the patient has undergone a prior surgical procedure in the planned treatment area. Areas with limited collateral blood flow have an increased risk of ischemia.
- Unintentional intravascular injection may lead to embolization, thrombosis, occlusion of the vessels, ischemia, necrosis or infarction at the implant site or in the area supplied by the blood vessels affected. Stop the injection immediately if blanching occurs or if a patient complains of unusual pain or exhibits any symptoms suggestive of inadvertent intravascular injection. Patients should receive prompt medical attention and possibly evaluation by an appropriate specialist doctor should an intravascular injection occur.
- Patients with bleeding disorders or patients using substances that affect platelet function, thrombolytics or anticoagulants may, as with any injection, experience increased bruising or bleeding at injection site.

 EST. 1981	Title 43CH2305 CSP Vital-Lido-Hand-2w	Doc id MA-57336
---	---	---------------------------

- Special care should be taken to avoid injection into tendons in the hand as it may weaken tendons and cause tendon rupture.
- This product should not be mixed with other products prior to injection

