##### 5.1.1 Overall Study Design

This is a randomized, multi-center, split-hand, subject-blinded study comparing pain, safety and effectiveness of Restylane Skinboosters Vital Lidocaine and Restylane Vital without lidocaine for improving appearance of the dorsal hands in Chinese subjects.

Written informed consent will be obtained before any study related procedure is performed. Subjects will be screened for eligibility within 14 days prior to study randomization on Day 1. The Screening Visit and Baseline Visit can be performed on the same day.

Each subject will receive treatment on Day 1 with Restylane Skinboosters Vital Lidocaine® in one hand and Restylane Vital in the opposite hand, as randomly assigned. Study treatment will be unblinded for the Treating Investigator. The first injection will always start in the right hand. No topical or local anesthetic or other pain-relieving medication should be used before all Visual Analogue Scale (VAS) assessments are completed. Ice for pain relief is allowed and should be applied equally on both hands before treatment, and an approximately two-minute ice application time per hand is recommended. Ice may also be used after all VAS evaluations have been completed. The second treatment, that is the injections in the left hand, will be performed after the treatment of the first (right) hand and the VAS assessment at T0 of the right hand is completed.

The subject will assess pain experienced directly after treatment on a 100 mm VAS at the end of each treatment (before massaging the treatment area). The time should be recorded in the electronic Case Report

 EST. 1981	Title 43CH2305 CSP Vital-Lido-Hand-2w	Doc id MA-57336
---	---	---------------------------

Form (eCRF) and the pain will thereafter be assessed by the subject at  $10\pm3$ ,  $20\pm3$ , and  $30\pm3$  minutes on the VAS after the treatment on the right and left hand, respectively.

After the treatment of each hand is finished, and after the T0 pain assessment is complete, massage can be performed on the treated area of that hand. It is recommended not to exceed five minutes of massage to avoid affecting subsequent VAS assessments. It is not necessary to massage both hands simultaneously.

A safety follow-up telephone call should be made 72 hours after treatment.

CCI

CCI

CCI

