#### 5.6.3 Control Medical Device (Comparator Product)

##### Restylane Vital

Restylane Vital will be provided in a glass syringe containing 1 ml of product. The study sites will be provided with 29 G needles Disposable sterile 29G x ½" TW needles for use in the study.

Composition:

- Crosslinked sodium hyaluronate\* 20 mg/mL
- Phosphate buffered saline pH 7 ad q.s. 1 mL

\*Produced from pharmaceutical grade sodium hyaluronate and crosslinking agent BDDE.

In terms of packaging, labelling, and storage of Restylane Vital, please see co-packed Restylane Vital Instructions for Use (IFU).

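### The lidocaine syringe can click and the comparator is not described as doing so, yet masking the sound is left to the investigator while the blinded subject scores the primary VAS

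*Protocol*

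**What the plan says.** Protocol 5.8.1.2 states that the subject is the only blinded party. It introduces a list of measures that sites are to apply to keep the subject blind. Two of them concern cues from the syringe:

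- Sound: "At the discretion of the investigator, the subject can listen to white noise/music in headphones during the treatment to cancel out the click sounds".
- Sight: "The injection will be performed behind a screen to prevent the subject from seeing the type of syringe used".

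The Protocol synopsis (Treatment Blinding) and SAP 4.2.5 repeat the discretionary headphone wording.

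On the devices, Protocol 5.7.3 discusses both products together but attributes the click system to one: "Restylane Skinboosters Vital Lidocaine has a built in dose-guide, Smart Click System, which when activated creates a clicking sound and haptic feedback". The comparator, in Protocol 5.6.3, is described more simply: "Restylane Vital will be provided in a glass syringe containing 1 ml of product". Its further instructions are left to its own IFU. Protocol 5.7.3.2 makes switching the system on a matter of preference, and adds: "The Smart Click System can be deactivated at any time by pushing the button in the finger grip upwards".

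The primary endpoint (Protocol 4.1, SAP 9.1.1) is the within-subject difference in VAS at T0, lidocaine minus no lidocaine, marked by the subject. The right hand is always first, and the left-hand injections "will be performed after the treatment of the first (right) hand and the VAS assessment at T0 of the right hand is completed".

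**The concern.** The plan recognises that the sound could unblind the subject and names a remedy, then leaves its use to each investigator. Masking can therefore differ between subjects and sites. The Treating Investigator, who knows the allocation, also handles the syringe and its click button.

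A sound that belongs to one product is a product-linked cue. If subjects attach a meaning to it, it can move a subjective score. Randomising which hand gets lidocaine balances hand and order effects, but not a cue that travels with the product.

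The outputs may not show whether this happened. The administration items named in SAP 10.2.7.1 and the per-protocol exclusions named in Protocol 6.3 and SAP 6.2 mention neither headphone use nor click status. Those lists are open-ended, so such items could be added, but nothing legible says they will be. No legible text plans to ask subjects which product they think each hand received.

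**Working it through.** **1. The plan's own sample size.** Protocol 6.1.1 and SAP 7 assume a mean difference of -10 mm, SD 25 mm and a one-sided one-sample t-test at 2.5%. Power is P(T > t₀.₉₇₅,ₙ₋₁), where T is noncentral t with n - 1 degrees of freedom and noncentrality 10·√n/25. The smallest n for 90% power is 68 (power 90.2%), as stated. Then 68 × 1.15 = 78.2, stated as about 80, and 80/0.90 = 88.9, stated as about 90. The planning figures reproduce.

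**2. How loud the cue could be.** Each click is 10 µL, and the allowed volume is 0.5 to 1 mL per hand. With the system on throughout, 500/10 = 50 to 1000/10 = 100 clicks per hand. With it off, none.

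**3. Which marks can be affected.** The right-hand T0 mark is complete before the left hand is injected, so a contrast between hands can act only on the left-hand mark. Suppose a subject takes clicking to mean the product that hurts less:

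- Lidocaine on the left: clicks follow a silent right hand, the left mark falls, and the difference (lidocaine minus comparator) becomes more negative.
- Comparator on the left: silence follows a clicking right hand, the left mark rises, and the difference again becomes more negative.

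Both orders push the same way, so they do not cancel. If subjects read the sound the opposite way, both push towards a positive difference.

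**4. What a mean shift would do.** The documents give no shift, so the values below are assumptions. The rejection probability is as in step 1, with noncentrality (net mean towards lidocaine)·√n/25. For example, at n = 80 and a 2.5 mm shift, noncentrality = 2.5 × 8.944/25 = 0.894.

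| Mean shift over all subjects | False-positive rate, true effect 0, shift towards lidocaine: n = 80 / n = 90 | Power, true effect -10 mm, shift away from lidocaine: n = 80 / n = 90 |
|---|---|---|
| 0 mm | 2.5% / 2.5% | 94.2% / 96.4% |
| 1 mm | 5.4% / 5.7% | 88.9% / 92.2% |
| 2.5 mm | 14.1% / 15.4% | 75.5% / 80.4% |
| 5 mm | 42.4% / 46.7% | 42.4% / 46.7% |

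At n = 80 and SD 25 mm, an observed mean of about -5.6 mm is enough for significance (1.990 × 25/8.944 = 5.56). A larger sample does not remove such a bias: under no true effect, the error at n = 90 is higher than at n = 80.

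**5. Dilution.** The shifts in the table are averages over everyone. If only a quarter of subjects were exposed and each shifted by 2 mm (both assumed), the mean shift is 0.25 × 2 = 0.5 mm. The false-positive rate is then 3.7% at n = 80 and 3.8% at n = 90.

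**The case against.** **The discretion may be meant sensibly.** The headphone line sits under an instruction that the measures are to be applied, and it states its purpose. Since the click system is optional, an investigator might read it as headphones only when clicks are on. That reading is plausible, but the text does not say it. An instruction to apply the measures and a discretion not to apply one of them still need reconciling.

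**A click does not identify lidocaine.** It shows only that the syringes differ. The Treating Investigator may not discuss the allocation, and product documents are kept from the subject. Both lower the chance that the sound carries meaning. This stands, and it is why the point is conditional. What subjects are told at consent is not available for review.

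**The error rates assume a mean shift.** Such a shift needs clicks on, no headphones and a meaning attached to the sound. This also stands; step 5 of the working shows how quickly limited exposure shrinks the effect.

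**Recording may exist elsewhere.** The eCRF and table shells are separate, Protocol 5.7.2.4 asks for changes in procedure to be recorded, and deviations will be listed. But choosing not to use a discretionary measure is neither a change in procedure nor a deviation, so these routes would not reliably capture it.

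**Headphones do not cover vibration.** The system also gives haptic feedback. The documents do not say whether the subject could feel it. This limits what headphones alone can achieve.

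**Universal headphones add a communication burden.** The protocol relies on subjects speaking up: "Stop the injection immediately if blanching occurs or if a patient complains of unusual pain". This is a real constraint on how masking is set up, though not a reason to leave it to discretion.

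**Conclusion.** The concern holds. The only measure against a product-linked sound is discretionary, while the measure against sight is not, and the person exposed to the sound scores the primary endpoint. No legible passage closes the gap.

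The effect on the result cannot be derived from the documents. It is zero if the clicks are off, masked or without meaning to the subject. Otherwise its direction is unknown and its size depends on how many subjects are exposed. Under the planning SD of 25 mm and 80 subjects, the hypothetical shifts give a false-positive rate from 3.7% (0.5 mm mean shift) to 42.4% (5 mm, half the planned effect). The conclusion also rests on the comparator having no click system; its description gives none, but its IFU is not among the documents. This is a point the sponsor should fix, held with medium confidence, because prevention is cheap and the bias could not be measured afterwards from the items now named.

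**What to change.** - **Masking rule.** In the Protocol synopsis, Protocol 5.8.1.2 and SAP 4.2.5, replace the discretionary headphone sentence with a uniform one: every subject wears headphones with noise or music during the injection of each hand, until that hand's T0 mark is made. Alternatively, state another way in which the sound difference between products is removed for all subjects. Either way, say whether the haptic feedback can reach the subject.
- **Recording.** Add two eCRF fields per hand, headphone use and click-system status, and name both in the SAP 10.2.7.1 summaries by study product.
- **Per-protocol set.** In Protocol 6.3 and SAP 6.2, name unmasked clicking as a deviation to be reviewed for exclusion. The FAS remains the primary set, so this affects only the supporting analysis.
- **Safeguard.** Describe how a subject wearing headphones can report unusual pain during injection, so that the warning in Protocol 3.5.5.1 still works.

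The cost is small: one wording change in three places, headphones that the protocol already foresees at three sites, two eCRF fields and one named deviation. The downsides are minor inconvenience for subjects and the need for a simple signal for pain.

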4.2.5 Allocation Concealment and Blinding

Only the subject will be blinded. Treating Investigator will not be blinded to the treatment assignment.

The Treating Investigator is not allowed to discuss treatment assignment per hand with the subjects. All documents with information on study products shall be kept in a separate binder not available to the subjects.

To ensure the subject is kept treatment-blind the following measures are to be employed at the study site when injecting: the same injection techniques, volume per injection point and similar total volume should be used for both hands.

At the discretion of the investigator, the subject can listen to white noise/music in headphones during the treatment to cancel out the click sounds from the syringe when injecting Restylane Vital Skinboosters Lidocaine.

The injection will be performed behind a screen to prevent the subject from seeing the type of syringe used.

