10.2.7 Measurements of Treatment Compliance

10.2.7.1 *Treatment Administration and Procedural Anesthetics*

Treatment administration endpoints that will be summarized by study product and overall include (but are not limited to): injection volume, injection technique, approximate number of injection sites, depth of injection, and needle size.

The number of subjects (n, %) with any post-treatment care will be summarized by study product and type of post-treatment care:

- None
- Massage
- Ice/cooling
- Other.

Listings of treatment administration and procedural anesthetics will be provided.

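### Headphone audio is optional, aimed at clicks from the lidocaine syringe, and not required to be the same for both hands, so the text permits a product-linked difference at the T0 pain rating

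*Protocol*

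**What the plan says.** On who is blinded, Protocol 5.8.1.2 states: "Only the subject will be blinded. Treating Investigator will not be blinded to the treatment assignment". It introduces the blinding precautions by saying that "the following measures are to be employed at the study site when injecting". One of these is audio, left to the investigator's discretion: "the subject can listen to white noise/music in headphones during the treatment to cancel out the click sounds from the syringe when injecting" the lidocaine product. The synopsis and SAP 4.2.5 carry the same rule. None of the three places says that the audio must be the same for both hands.

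Other conditions of the injection do have a matching rule. SAP 4.2.5, following Protocol 5.8.1.2, says that "the same injection techniques, volume per injection point and similar total volume should be used for both hands". Protocol 5.1.1 says: "Ice for pain relief is allowed and should be applied equally on both hands before treatment".

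Only the lidocaine syringe is described as having the clicking dose guide (Protocol 5.7.3; the comparator description in 5.6.3 mentions none). Activating it is optional (Protocol 5.7.3.2, step 6). The right hand is always injected first, and its T0 VAS is completed before the left hand is treated (Protocol 5.1.1).

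SAP 10.2.7.1 names the treatment-administration items to be summarised as "injection volume, injection technique, approximate number of injection sites, depth of injection, and needle size". Audio is not named there, nor among the per-protocol exclusions in Protocol 6.3 and SAP 6.2. Both lists are open-ended.

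**The concern.** The primary endpoint is a subjective rating, taken hand by hand and analysed as a paired difference. Such a comparison is protected only if everything other than the product is the same in the two hands, or varies independently of product. The plan applies that principle to ice, technique and volume but not to audio, although audio is the measure whose stated reason relates to one product only. The choice also lies with someone who knows which hand receives that product.

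Because the hands are treated in sequence, putting headphones on for one hand and not the other is practicable. Two consequences are possible. The subject may notice that the hands are handled differently, which weakens the blind. And if listening to music or noise lowers the pain rating, audio on the lidocaine hand alone would lower that hand's T0 score and make the difference (lidocaine minus comparator) more negative, which is the direction of success. Randomising product to hand balances side and order. It does not balance something that goes with the product.

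**Working it through.** **The plan's own figure.** Inputs from Protocol 6.1.1 and SAP 7: mean difference -10 mm, SD 25 mm, one-sided 2.5%, one-sample t-test, 90% power, 68 subjects.

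- Normal approximation: (25 × (1.960 + 1.282) / 10)² = 65.7, so 66.
- Exact noncentral t: at n = 68 the noncentrality is (10/25) × √68 = 3.30 and power is 90.2%; n = 67 gives 89.7%. The stated 68 is reproduced.
- 68 × 1.15 = 78.2, taken as about 80; 80/0.9 = 88.9, taken as about 90.

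The sample size is sound, and this point does not alter it.

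**How small a shift matters.** The observed mean needed for significance is -t(0.975, n-1) × 25/√n:

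- n = 80: 1.990 × 25/8.944 = 5.6, so about -5.6 mm.
- n = 90: 1.987 × 25/9.487 = 5.2, so about -5.2 mm.

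**Illustration of an average bias.** Let b be the average shift in the T0 difference caused by unequal audio: the share of subjects with audio on the lidocaine hand only, times the mean reduction in VAS that audio produces in them. Neither factor is in the documents, and b is zero if either factor is zero. The range 0 to 3 mm is assumed. With no true lidocaine effect, the chance that the planned test rejects is the upper tail of a noncentral t beyond t(0.975, n-1), with n-1 degrees of freedom and noncentrality (b/25) × √n:

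| Assumed b (mm) | Noncentrality, n = 80 / 90 | Rejection, n = 80 | Rejection, n = 90 |
|---|---|---|---|
| 0 | 0 / 0 | 2.5% | 2.5% |
| 1 | 0.36 / 0.38 | 5.4% | 5.7% |
| 2 | 0.72 / 0.76 | 10.5% | 11.3% |
| 3 | 1.07 / 1.14 | 18.4% | 20.2% |

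**Does the planned analysis correct for it?** No. The primary analysis is an unadjusted one-sample t-test on the FAS (SAP 10.4.2 and 10.4.6.1). The per-protocol analysis is a sensitivity analysis only (SAP 10.4.3).

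**The case against.** A reader might infer that the protocol directs audio for the lidocaine hand only. It does not. The audio is allowed during the treatment, which can mean the whole session. The words about injecting the lidocaine product can be read as saying when the clicks occur, not when the headphones go on. The precaution exists to keep the subject blind, and audio on one hand only would work against that aim, so a sensible site might well use it for both. The click system is itself optional; where it is off, there is nothing to mask and no stated reason for audio.

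Nor do the documents say that music or white noise lowers a VAS score. The existence, direction and size of a distraction effect are all assumptions. The rejection rates above also suppose that lidocaine does nothing, whereas the two earlier filler studies cited for the sample size showed differences of 33.0 and 32.0 mm. The plan discounts these to 10 mm.

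All of this stands as a limit on the point. It does not close the gap. Use on one hand remains a permitted reading, the text is unclear on whether the measure is required or discretionary, and the decision rests with an unblinded person. The favourable interpretation has to be supplied by the site, whereas for ice, technique and volume the plan supplies it.

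**Conclusion.** The point holds as an avoidable gap in the blinding rule. The plan allows, without prescribing, a difference between hands that would follow the product and that randomisation would not cancel. If it occurred, and if audio reduces reported pain, the T0 difference would be biased towards success. A mean bias of 1 to 3 mm would be 10 to 30% of the planned 10 mm effect.

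Two stronger conclusions are not supported. A reader might infer that the trial's type I error is inflated to one of the tabulated values. Those values are what-ifs resting on an assumed b and a lidocaine effect of exactly zero; at b = 0 the error is the nominal 2.5%. If the true effect were near that of the two cited studies, the success decision would hardly be affected, though the estimate could still be biased. A reader might also infer that unequal audio could not be examined afterwards. The administration and exclusion lists are open-ended and the eCRF is not among the documents, so it may be captured; the plan simply does not secure this.

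The case for acting rests on the low cost of the change and the subjective endpoint, not on evidence that bias will occur.

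**What to change.** In Protocol 5.8.1.2, the synopsis and SAP 4.2.5, state that the audio condition is identical for both hands of a subject, from the start of the right-hand injection until the left-hand T0 VAS is marked. Where the SmartClick system is activated, the audio is used for both hands, so that the clicks are masked without creating a difference between hands. Where it is not activated, the same audio is used for both hands or none for either. The choice must therefore be made before the right hand is injected, whichever product that hand receives. Requiring audio for the lidocaine hand alone would not be a repair: it would make the difference systematic.

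Record audio use per hand in the eCRF, and name unequal use in Protocol 6.3 and SAP 6.2 as a deviation to be assessed for exclusion from the per-protocol set. That supports only the sensitivity analysis; the equal-use rule is what protects the FAS primary analysis. With equal use, any distraction cancels in the paired difference provided it acts alike in both hands.

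Cost: one protocol sentence with matching text in the synopsis and SAP, one eCRF field per hand, and headphones during both injections in the subjects affected. The sample size does not change.
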